## 10.6 Efficacy Subgroup Analysis

The subgroup analyses will be performed based on the ITT and mITT-GT-VF populations. The number and percentage of subjects with SVR12 will be presented for the following subgroups:

- HCV genotype and subtype (as defined in Section 10.8);
- Sex (male or female);
- Age (< 65 or ≥ 65 years) and (< 75 or ≥ 75 years);
- Race (White, Black/African-American, Asian, or other) and (black or non-black);
- Ethnicity (Hispanic or Latino, Not Hispanic or Latino);
- Geographic region (North America, Europe, or ROW);
- Baseline BMI (< 30, or ≥ 30 kg/m^2);
- Baseline HCV RNA level (< 800,000 or ≥ 800,000 IU/mL; < 1,000,000 or ≥ 1,000,000 IU/mL);
- Baseline Child-Pugh score (5, 6, or > 6)
- Baseline platelet count (< 100 or ≥ 100 × 10^9/L; < 150 or ≥ 150 × 10^9/L);
- Baseline albumin (< 35 or ≥ 35 g/L);
- Baseline FibroTest (< 0.75 or ≥ 0.75);
- Baseline APRI (≤ 1, > 1 to ≤ 2, or > 2);
- Baseline FIB-4 (< 1.45, ≥ 1.45 to ≤ 3.25, or > 3.25);
- Baseline AST/ALT ratio (≤ 1 or >1);
- Baseline total bilirubin (< 34.2 or ≥ 34.2 umol/L);
- Baseline creatinine clearance (< 60, ≥ 60 to < 90, or ≥ 90 mL/min);
- Baseline eGFR (< 60, ≥ 60 to < 90, or ≥ 90 mL/min/1.73 m^2);
- Subject on stable opiate substitution (yes/no);
- History of diabetes (yes/no);
- Concomitant use of Proton Pump Inhibitors (PPIs) (yes/no).

The 2-sided 95% confidence interval using Wilson's score method will be produced if there are at least 10 subjects in the subgroup.

In addition, stepwise logistic regression will be performed on SVR12 with all subgroup variables used as predictors of response based on the mITT-GT-VF population. Some

variables will be treated as continuous to decrease the chance of separation or quasi-separation and some variables may be eliminated if missing for many subjects.

## 10.7 Additional Efficacy Analyses

The following additional efficacy analyses will be performed in the ITT population:

- The percentage of subjects with HCV RNA < LLOQ at each post-baseline visit in the Treatment Period (using data as observed);
- The percentage of subjects who achieve SVR4 (HCV RNA < LLOQ 4 weeks after the last actual dose of study drug);
- The percentage of subjects who achieve SVR24 (HCV RNA < LLOQ 24 weeks after the last actual dose of study drug);
- The percentage of subjects who experience post-treatment relapse after achieving SVR12 (**Relapse24**).

In the above analyses for SVR, virologic failure, and relapse, the percentage of subjects with a two-sided 95% Wilson score interval will be summarized. Imputations for missing data will be performed as described in Section 7.0 for analysis of SVR, where a missing response will be imputed as a failure after performing the described imputation. All other endpoints will be presented using data as observed.

A summary of the subjects who completed treatment and relapsed (defined as **Relapseoverall**) will be prepared displaying the number of subjects relapsing overall and by SVR visit window (within the SVR4, SVR12, SVR24 windows or after SVR24 window), including the subject number and the SVR visit window corresponding to the first occurrence of relapse. A similar listing will be prepared for subjects who prematurely discontinued treatment and relapsed after having HCV RNA < LLOQ at their Final Treatment Visit.

A listing of subjects in the ITT population excluded from the relapse denominator (e.g., study drug duration < 52 days for subjects assigned to 8 weeks of treatment) will be provided, as applicable.

The number and percentage of subjects who do not achieve SVR12 will be summarized by reason for non-response (as defined in Section 10.1). A listing of subject numbers and reason for non-response will be prepared. A similar summary and listing will be prepared for subjects who do not achieve SVR24.

The concordance between SVR12 and SVR24 will be assessed by the agreement between SVR12 and SVR24 and the positive predictive value (PPV) and negative predictive value (NPV) of SVR12 on SVR24. The agreement between SVR12 and SVR24 is a percentage defined as the number of subjects achieving both SVR12 and SVR24 and the number of subjects where both SVR12 and SVR24 are not achieved. The PPV of SVR12 on SVR24 is the proportion of subjects who achieve SVR12 and SVR24 out of all subjects who achieved SVR12. The NPV of SVR12 on SVR24 is the proportion of subjects who neither achieve SVR12 nor SVR24 out of all subjects who did not achieve SVR12. Similarly, the concordance between SVR4 and SVR12 will be summarized.

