### **6.3 Missing Data Imputation**

#### **Missing Data Imputation for SVR**

HCV RNA values will be selected for analysis based on the analysis windows defined in Section 6.2.

For analyses of SVR, subjects missing visit values will have backward imputation applied, if possible. For backward imputation, if the nearest HCV RNA value after the SVR window is unquantifiable or undetectable, then it will be used to impute the HCV RNA value in the SVR window. If a subject is missing an HCV RNA value within the appropriate SVR window after performing backward imputation, then this value will be imputed with an HCV RNA value from a local laboratory if present; otherwise, the HCV RNA value will be missing. Subjects with missing HCV RNA data in the analysis window, after imputations, will be imputed as a failure.

Regardless of the imputation method described above, if a subject starts another treatment for HCV, then all HCV RNA values for this subject measured on or after the start date of the new HCV treatment will be excluded from analyses. The subject will be considered a failure for summaries of viral response at all time points after the start of the new HCV treatment.

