## 10.0 Efficacy Analysis

### 10.1 General Considerations

All efficacy analyses will be performed on the ITT population, unless otherwise specified.

Missing data will be imputed as described in Section 6.3 for analyses of the HCV RNA endpoints of SVR.

Plasma HCV RNA levels will be determined for each sample collected by the central laboratory using the Roche COBAS® AmpliPrep/COBAS® TaqMan® Quantitative HCV Test, v2.0. The lower limit of detection (LLOD) and lower limit of quantification (LLOQ) for this assay (regardless of genotype) are both 15 IU/mL.

HCV RNA results that are detectable but not quantifiable are reported as "< 15 IU/ML HCV RNA DETECTED" and those that are undetectable are reported as "HCV RNA NOT DETECTED" in the database.

The notation "HCV RNA < LLOQ" is used to represent all HCV RNA values < 15 IU/mL, including values reported as "HCV RNA NOT DETECTED" or "< 15 IU/ML HCV RNA DETECTED." HCV RNA  $\geq$  LLOQ are all quantifiable values of 15 IU/mL or greater.

IL28B rs12979860 will be resulted as C/C, C/T, or T/T by the central laboratory.

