**On-Treatment Virologic Failure = Breakthrough or EOT Failure.**

**SVR4** = HCV RNA  $<$  LLOQ in the SVR4 window (4 weeks after the last actual dose of study drug) without any confirmed quantifiable ( $\geq$  LLOQ) post-treatment value before or during that SVR window.

**SVR12** = HCV RNA  $<$  LLOQ in the SVR12 window (12 weeks after the last actual dose of study drug) without any confirmed quantifiable ( $\geq$  LLOQ) post-treatment value before or during that SVR window.

**SVR24** = HCV RNA  $<$  LLOQ in the SVR24 window (24 weeks after the last actual dose of study drug) without any confirmed quantifiable ( $\geq$  LLOQ) post-treatment value before or during that SVR window.

**Relapse12** = confirmed HCV RNA  $\geq$  LLOQ between end of treatment and 12 weeks after last actual dose of study drug (up to and including the SVR12 assessment time point) for a subject with HCV RNA  $<$  LLOQ at Final Treatment Visit who completed treatment and has post treatment HCV RNA data available, excluding reinfection as described below.

**Relapse24** = confirmed HCV RNA  $\geq$  LLOQ during SVR24 window among subjects who achieved SVR12 and have HCV RNA data available during the SVR24 window, excluding reinfection as described below.

**Relapseoverall** = confirmed HCV RNA  $\geq$  LLOQ between end of treatment and up to and including the last HCV RNA measurement collected in the PT Period for a subject with HCV RNA  $<$  LLOQ at Final Treatment Visit who completed treatment and has post treatment HCV RNA data available, excluding reinfection as described below.

Only subjects who have at least one post-treatment HCV RNA value will be included in analyses of relapse. For relapse analyses, the completion of treatment is defined as a study drug duration  $\geq$  52 days for subjects assigned to 8 weeks of treatment. If the regimen is extended to 12 weeks for some subjects, then those subjects will be considered completers if they have a study duration  $\geq$  77 days. If the last available post-treatment value is  $\geq$  LLOQ, then the subject will be considered a relapse (i.e., will not require confirmation).

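### The SVR12/SVR24 concordance table counts SVR12 responders with no SVR24 data as discordant, so PPV and agreement fall with loss to follow-up

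*SAP*

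**What the plan says.** SAP 10.7 plans a concordance summary of SVR12 against SVR24, and likewise of SVR4 against SVR12. PPV is the proportion with both SVR12 and SVR24 "out of all subjects who achieved" SVR12. NPV is the mirror image among all subjects who did not achieve SVR12. Agreement is called a percentage, but only its numerator is given: both achieved plus neither achieved.

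The paragraph does not say which SVR values enter. The general rules do:

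- SAP 10.1: "Missing data will be imputed as described in Section 6.3 for analyses of the HCV RNA endpoints of SVR".
- SAP 6.3: "For analyses of SVR, subjects missing visit values will have backward imputation applied, if possible". If the nearest value after the window is unquantifiable or undetectable, "then it will be used to impute the HCV RNA value in the SVR window". Failing that, a local-laboratory value is used.
- SAP 6.3, last step: "Subjects with missing HCV RNA data in the analysis window, after imputations, will be imputed as a failure".
- SAP 10.7 repeats the last step for SVR: "where a missing response will be imputed as a failure after performing the described imputation". It cites Section 7.0 for the method, but Section 7.0 covers demographics and baseline data; the rules are in 6.3.

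SAP 10.7 then adds: "All other endpoints will be presented using data as observed". Concordance is named on neither side of that line.

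Relapse24 (SAP 10.1) is handled differently. It is restricted to subjects who achieved SVR12 "and have HCV RNA data available during the" SVR24 window.

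**The concern.** A PPV of SVR12 for SVR24 is read as the chance that a Week 12 response lasts to Week 24. If a responder who simply has no Week 24 value enters as a failure, the shortfall from 100% mixes late loss of response with loss to follow-up, and the statistic cannot separate them. The same report could then show no late relapse beside a PPV clearly below 100%.

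Missing data at the earlier time point act in the other direction. A missing SVR12 value is usually filled from the later one, or both are set to failure, and either way the pair is scored as agreeing. At stake is the reading of one descriptive table, not the primary or key secondary results.

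**Working it through.** The documents state no concordance figure, so there is none to reproduce. The check classifies the possible data patterns under the SAP rules and then sizes the effect.

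**Patterns for SVR12 and SVR24** (setting aside local-laboratory values and rare unconfirmed results)

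| Data | Scored as |
|---|---|
| SVR12 achieved; SVR24 missing, no later unquantifiable value | success/failure: discordant |
| SVR12 missing; next value unquantifiable | success/success: concordant |
| SVR12 missing; later value quantifiable | failure/failure: concordant |
| Both missing, nothing later | failure/failure: concordant |

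**Inputs.** N = 330 and a 97% ITT SVR12 rate (Protocol 8.2): 330 × 0.97 = 320 responders, 10 non-responders. The share of responders missing SVR24 is assumed at 1%, 2%, 3% or 5%, which is 3, 6, 10 or 16 subjects after rounding.

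**Formulas.** With m missing and r late relapses:

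- PPV under the SAP rules = (320 − m − r)/320
- PPV on observed pairs = (320 − m − r)/(320 − m)
- Agreement under the SAP rules = (320 − m − r + 10)/330, taking all subjects as the denominator (an assumption, since the SAP gives none) and all 10 non-responders as SVR24 failures

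**No late relapse (r = 0)**

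| m | PPV, SAP rules | PPV, observed pairs | Agreement, SAP rules |
|---|---|---|---|
| 0 | 320/320 = 100% | 100% | 330/330 = 100% |
| 3 | 317/320 = 99.1% | 100% | 327/330 = 99.1% |
| 6 | 314/320 = 98.1% | 100% | 324/330 = 98.2% |
| 10 | 310/320 = 96.9% | 100% | 320/330 = 97.0% |
| 16 | 304/320 = 95.0% | 100% | 314/330 = 95.2% |

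**One late relapse, m = 10.** PPV under the SAP rules is 309/320 = 96.6%; on observed pairs it is 309/310 = 99.7%. Relapse24 would be 1/310 = 0.3%, which matches the observed-pairs figure.

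**Share of discordance due to missing data.** A second scenario assumes 2% virologic failure by Week 12, 1% missing at Week 12 with half returning, and 0.3% late relapse. The number observed without failure at Week 12 is 330 − 6.6 − 3.3 = 320.1. At 1% loss, 3.2 are missing and 320.1 × 0.99 × 0.003 = 0.95 relapse, so missing data make up 3.2/4.15 = 77% of discordant subjects. At 3% loss the share is 91%. If late relapse is 1% instead, the shares are 50% and 76%.

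**NPV.** The SVR24 definition in SAP 10.1 rules out anyone with an earlier confirmed quantifiable post-treatment value, so a confirmed relapse by Week 12 cannot become an SVR24 success. If, as an assumption, 4 of the 10 non-responders have no data, NPV is 10/10 under the SAP rules and 6/6 among those measured. Both are 100%.

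**The case against.** The strongest reply is that the SAP already answers the durability question on observed data. Relapse24 is a listed additional analysis, overall relapse is tabulated by window, and reasons for SVR24 non-response keep relapse after SVR12 and missing data in separate, mutually exclusive categories. A reader who sees a PPV below 100% can look there for the cause. This stands, and it is why the point is minor. A reader might take the concordance table to be the trial's check that SVR12 is durable; the documents do not give it that role.

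Second, the concordance paragraph never says that imputed values are used, and the line on presenting other endpoints as observed could be read to cover it. That is fair: imputed values are the default reading, inferred from the general rules. The ambiguity is itself a reason to state the rule.

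Third, the loss may be small. The SVR24 window is wide (Study Drug End Days 127 to 210, SAP Table 2), and later or local values are tried before failure is imputed. The nearest documented figures concern follow-up to SVR12 only: 1.2% non-virologic failure (29/2369) and 2 of 182 historical subjects (1.1%) with missing SVR12 data. At about 1% loss the PPV gap is about one percentage point. This also stands.

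Fourth, the PPV effect can only understate durability. That is correct; it cannot create a false claim that responses last.

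**Conclusion.** The point holds as a minor one. Under the default SVR rules, an SVR12 responder with no SVR24 value after imputation lowers PPV and agreement, and the result can part from Relapse24 for no virologic reason. The gap in PPV is roughly the proportion of responders without SVR24 data: about 1 to 5 percentage points over the assumed 1% to 5%, and none at zero loss.

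Two stronger readings are tempting and are not supported. One is that the table measures loss to follow-up instead of prediction. How far missing data dominate depends on assumed loss and late-relapse rates, neither of which the documents give. The other is that subjects with no data inflate NPV. NPV stays near 100% with or without them, because of how SVR24 is defined.

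The analysis has no success criterion, lies outside the four-step sequence in SAP 10.2, and is not among the additional endpoints in Protocol 8.1.2.5. No tested result changes.

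**What to change.** In SAP 10.7:

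- Compute agreement, PPV and NPV among subjects with observed HCV RNA status in both windows, without backward imputation and without missing-as-failure.
- Keep subjects already classed as virologic failures by SVR12 as SVR24 failures. Without this, those who start another HCV treatment would drop out, because SAP 6.3 excludes their later HCV RNA values.
- State the denominator for agreement.
- Apply the same rule to SVR4 against SVR12.
- Correct the imputation cross-reference from Section 7.0 to 6.3.
- Keep the version with imputed values as a supportive table.

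The cost is a short SAP edit and one re-run table, with no new data. The downside is slightly smaller denominators.

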## 10.8 Resistance Analyses

For all subjects, full length NS3/4A or NS5A from baseline samples will be sequenced by next generation sequencing (NGS). For subjects who experience virologic failure (on-treatment virologic failure or post-treatment relapse as defined in Section 10.1), full length NS3/4A and NS5A genes from the first sample after virologic failure with HCV RNA  $\geq$  1000 IU/mL will be sequenced by NGS. An appropriate subtype specific prototypic reference sequence will be used for comparison with sequences from samples. Subjects who experience virologic failure (VF) will be referred to as subjects in the primary virologic failure (PVF) population, and a listing by subject that includes HCV genotype/subtype, IL28B genotype, reason for SVR12 non-response, time point(s) sequenced as closest to time of VF, and HCV RNA value at the VF time point(s) will be produced for these subjects. In addition, all listings described below will display HCV genotype/subtype and reason for SVR12 non-response in the subject identifier for each subject. A separate listing will summarize all subjects in the PVF population for whom no sequencing was performed (e.g., lost to follow-up while HCV RNA  $\leq$  1000 IU/mL).

Subjects treated with study drug who do not achieve SVR12 due to reasons other than virologic failure (prematurely discontinued study drug with no on-treatment virologic failure, HCV reinfection, missing SVR12 data, or other reasons as described in Section 10.1, Reasons for SVR12 Non-Response), but have a time point with HCV RNA  $\geq$  1000 IU/mL after treatment discontinuation will have the sample at that time point sequenced. These subjects will be referred to as the non-PVF population. A listing of all subjects in the non-PVF population with post-baseline sequencing available will be created that is similar to the listing of subjects in the PVF population with post-baseline sequencing available.

Included time points for analyses on samples from subjects who do not achieve SVR12 are 1) the sample closest in time after failure/discontinuation with an HCV RNA level of  $\geq$  1000 IU/mL, and 2) 24 weeks post-DAA treatment, provided that resistance-associated substitutions were detected by NGS at the time of HCV virologic failure/treatment discontinuation.

For each DAA target, signature amino acid positions and a key subset of amino acid positions are listed in Table 6. Appropriate subtype-specific prototypic reference sequence will be used for comparison with sequences from samples.

**Table 6. Signature Amino Acid Positions and the Key Subset of Amino Acid Positions**

Target	Signature Amino Acid Positions	Key Subset of Amino Acid Positions
GT1 NS3	36, 43 (GT1a only), 54, 55, 56, 80, 107, 122, 132 (GT1a only), 155, 156, 158, 168, 170, 175 (GT1b only)	155, 156, 168 (all GTs)
GT2, 3, 4, 5, 6 NS3	36, 43, 54, 55, 56, 80, 155, 156, 166 (GT3 only), 168	
GT1 NS5A	24, 28, 29, 30, 31, 32, 54 (GT1b only), 58, 62, 92, 93	24, 28, 30, 31, 58, 92, 93 (all GTs)
GT2, 3, 4, 5, 6 NS5A	24, 28, 29, 30, 31, 32, 58, 92, 93	

The following definitions will be used in the resistance analyses:

- Baseline polymorphism: a polymorphism by NGS in a baseline sample ( $\geq 2\%$  or  $\geq 15\%$  prevalence within a subject's viral population depending on polymorphism frequency threshold utilized) that was not present in the appropriate prototypic reference amino acid sequence for a given DAA target (NS3/4A or NS5A).
- Polymorphism/substitution at a signature amino acid position: polymorphism (relative to reference) present in a baseline sample or substitution (relative to baseline) present in post-baseline sample at a signature amino acid position.
- Post-baseline substitution: an amino acid substitution in a post-baseline time point sample that was not detected at baseline ( $< 2\%$ ) in the subject and is detectable in  $\geq 2\%$  of the sequences from the post-baseline sample.
- Enriched substitution: substitution present in both the baseline and a post-baseline sample whose prevalence in the post-baseline sample is at least 20 percentage points greater than the prevalence in the baseline sample [(post-baseline % – baseline %)  $\geq 20$ ].
- Treatment-emergent substitution: A post-baseline substitution or an enriched substitution.

**Analysis 1:** The following analyses will be provided for all subjects, separated by HCV subtype:

- A listing of all baseline polymorphisms (2% detection threshold) at signature amino acid positions for each DAA target (NS3/4A and NS5A) (ITT).
- A listing of all baseline polymorphisms (15% detection threshold) at non-signature amino acid positions for each DAA target (NS3/4A and NS5A) for subjects in the PVF population.
- A by subject listing of baseline polymorphisms (15% detection threshold) at signature amino acid positions in subjects with polymorphisms across both NS3 and NS5A, or those with multiple baseline polymorphisms within any one target (NS3/4A or NS5A).

- The number and percentage of subjects with baseline polymorphisms at signature amino acid positions at detection thresholds of 2% and 15% (ITT). This table includes prevalence of each baseline polymorphism, and a summary of number of subjects with polymorphisms in NS3 only, in NS5A only, any in NS3, any in NS5A, any in NS3 or NS5A, any in NS3 + NS5A.
- Total number and percentage of subjects with baseline polymorphisms at a key subset of amino acid positions in NS3 only, in NS5A only, any in NS3, any in NS5A, any in NS3 or NS5A, any in NS3 + NS5A, by subtype, and total (include all subtypes) (ITT).
- Total number and percentage of subjects with baseline polymorphisms at a key subset of amino acid positions in NS3 only, in NS5A only, any in NS3, any in NS5A, any in NS3 or NS5A, any in NS3 + NS5A, by genotype, and total (include all genotypes) (ITT).

**Analysis 2:** The impact of baseline polymorphisms on treatment outcome will be assessed for the mITT-GT-VF population as follows: for each polymorphism, the SVR12 rate will be calculated for subjects with and without the polymorphism and the 2 rates will be compared. Analysis will be grouped by HCV subtype and DAA target (NS3/4A or NS5A).

The following will be included in the analyses of impact of baseline polymorphisms on treatment outcome:

- For each signature amino acid position, presence of any polymorphism at that position (vs no polymorphism at that position), using detection thresholds of both 2% and 15%.
- Each individual polymorphism at each signature amino acid position (vs not that polymorphism) using detection thresholds of 2% and 15%.
- Polymorphism at each non-signature amino acid position (vs. no polymorphism at that position) at a detection threshold of 15%.

**Analysis 3:** In subjects with or without polymorphisms in NS3 only, in NS5A only, any in NS3, any in NS5A, any in NS3 or NS5A, any in NS3 + NS5A at the key subset of

amino acid positions at 15% detection threshold, the SVR12 rate will be calculated for the mITT-GT-VF population, and the rates with or without polymorphisms will be compared using Fisher's exact test. Analysis will be separated by HCV subtype. The following tables will be provided:

- Comparison of SVR12 rates by subtype, and total (include all subtypes)
- Comparison of SVR12 rates by genotype, and total (include all genotypes)

**Analysis 4:** The following analyses will be performed for subjects who do not achieve SVR12 and who have post-baseline resistance data available:

- Listings by subject of all treatment-emergent substitutions relative to the baseline amino acid sequences will be provided for each DAA target (NS3/4A and NS5A).
- Listings by subject and time point of all post-baseline substitutions at signature amino acid position relative to the baseline amino acid sequence will be provided for each DAA target (NS3 and NS5A).
- The persistence of post-baseline variants at signature resistance-associated amino acid positions for each target (NS3 and NS5A) from subjects will be assessed at Post-Treatment Week 24. Listings by subject and time point of all treatment-emergent variants will be provided for each DAA target (NS3 and NS5A).

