The association between baseline polymorphisms and treatment outcome in subjects who received GLE 300 mg QD with PIB 120 mg QD in the registrational or supportive Phase 2 studies was evaluated by conducting an integrated analysis of baseline sequence data. Next-generation sequencing (NGS) was conducted on all baseline samples at 15% detection threshold at key amino acid positions 155, 156, and 168 in NS3, and 24, 28, 30, 31, 58, 92, and 93 in NS5A.

In subjects who were TN or TE-PRS, baseline polymorphisms in NS3 were detected in 1.1% (9/845), 0.8% (3/398), 1.6% (10/613), 1.2% (2/164), 41.9% (13/31), and 2.9% (1/34) of subjects with HCV genotype 1, 2, 3, 4, 5 and 6 infection, respectively. Baseline polymorphisms in NS5A were detected in 26.8% (225/841), 79.8% (331/415), 22.1% (136/615), 49.7% (80/161), 12.9% (4/31), and 54.1% (20/37) of subjects with HCV genotype 1, 2, 3, 4, 5, and 6 infection, respectively.

The presence of baseline polymorphisms in NS3 and/or NS5A did not have an impact on SVR₁₂ rates for GT1-, 2-, 4-, 5-, or 6-infected subjects. Baseline polymorphisms in NS3

did not have an impact on SVR₁₂ in GT3-infected subjects. Among baseline polymorphisms in NS5A in GT3-infected subjects, Y93H did not have an impact on SVR₁₂ rates except in treatment-experienced non-cirrhotic subjects receiving 12 weeks of treatment. A30K in NS5A at baseline was associated with lower SVR₁₂ rates among non-cirrhotic treatment-naïve subjects receiving 8 weeks of treatment and treatment-experienced subjects receiving 12 weeks of treatment, but had no impact on SVR₁₂ rates in treatment-naïve non-cirrhotic subjects receiving 12 weeks of treatment. The SVR₁₂ rates in subjects with A30K at baseline were 77.8% (14/18), 25.0% (1/4), and 92.9% (13/14) among treatment-naïve subjects receiving 8 weeks, treatment-experienced subjects receiving 12 weeks, and treatment-naïve subjects receiving 12 weeks of treatment, respectively. Given the A30K prevalence of 6.3% among GT3-infected subjects, the difference in SVR₁₂ attributable to the impact of A30K between the 8 and 12 weeks treatment duration is < 1%. Among treatment-experienced non-cirrhotic or cirrhotic subjects receiving 16 weeks of treatment, the impact of A30K is unclear due to the low prevalence of the polymorphism in this arm of the study.

Integrated Safety Results

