5.6.4.2 GLE and PIB Dose and Treatment Duration

GLE/PIB 300 mg/120 mg QD regimens with 8-week and 12-week durations were evaluated in non-cirrhotic subjects in registrational trials. Efficacy of 8-week treatment duration is established for GT1-, GT2- and GT3- infected non-cirrhotic subjects [R&D/16/0144, R&D/15/1230]. Fifty-two non-cirrhotic GTs 4, 5, or 6-infected subjects received 8-weeks of GLE/PIB and no virologic failure was observed. Overall, these results conclude that 8-weeks of GLE/PIB 300 mg/120 mg dose is efficacious for non-cirrhotic GT 1 - 6-infected subjects.

Based on modeling and simulations, assuming no subjects experience non-virologic failures, following 8 weeks of GLE/PIB in treatment-naïve HCV-infected subjects with compensated cirrhosis, the predicted SVR₁₂ rate is approximately 98% for GT1, 2, 4, 5, and 6-infected subjects, and approximately 92% for GT3-infected subjects.

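### The pooled total rows of the polymorphism comparison are not stratified by genotype, which slightly biases the NS5A result toward polymorphisms looking protective

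*SAP*

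**What the plan says.** SAP 10.8 Analysis 3 works in the mITT-GT-VF population. It computes SVR12 with and without polymorphisms at the key positions (NS3 only, NS5A only, any in either target, and so on), "and the rates with or without polymorphisms will be compared using Fisher's exact test". The next sentence adds: "Analysis will be separated by HCV subtype". Two tables follow, one by subtype and one by genotype, each ending in a pooled total; the second is specified as a comparison of SVR12 "rates by genotype, and total (include all genotypes". Protocol 8.1.4 plans the same two tables and the same test. Neither document names a stratified or adjusted method for the totals.

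Protocol 3.0 gives the prevalences from the registrational program, in the order GT1 to GT6: "Baseline polymorphisms in NS5A were detected in 26.8% (225/841), 79.8% (331/415), 22.1% (136/615), 49.7% (80/161), 12.9% (4/31), and 54.1% (20/37) of subjects", and for NS3: "baseline polymorphisms in NS3 were detected in 1.1% (9/845), 0.8% (3/398), 1.6% (10/613), 1.2% (2/164), 41.9% (13/31), and 2.9% (1/34) of subjects". Protocol 5.6.4.2 gives the modelled 8-week response, leaving out non-virologic failures: the predicted SVR12 "rate is approximately 98% for GT1, 2, 4, 5, and 6-infected subjects, and approximately 92% for GT3-infected subjects".

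**The concern.** A crude pooled comparison is confounded when a third factor is related to both exposure and outcome. Genotype meets both conditions on the sponsor's own figures. GT3 has a low NS5A prevalence and the lowest predicted response, so GT3 subjects are over-represented among those without a polymorphism and pull that group's SVR12 down. A polymorphism that does nothing then looks mildly protective, and one that does harm in GT3 looks less harmful than it is.

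No other planned analysis corrects for this. Analysis 2 is grouped by subtype and has no stratified summary. The stepwise logistic regression in SAP 10.6 includes genotype, but polymorphisms are not among its predictors. About ten virologic failures are expected in all (270 × 2% + 60 × 8% = 10.2), so the individual rows will be sparse and the total row will draw the eye.

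**Working it through.** **Inputs.** Protocol 8.2 gives 270 non-GT3 and 60 GT3 subjects. Failure rates are 2% and 8%, from the 98% and 92% predictions. Those predictions leave out non-virologic failures, as mITT-GT-VF does (SAP 5.1.4), so they fit this analysis. The mix within the 270 is not stated. Mix A, an assumption, scales the cirrhotic column of protocol Table 2 (GT1 101, GT2 35, GT4 20, GT5 2, GT6 7; total 165) to 270.

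**The plan's own figures.** The stated counts give the stated percentages, for example 331/415 = 79.8% and 136/615 = 22.1%. All twelve NS3 and NS5A values reproduce.

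**NS5A row with no effect in any genotype (mix A).** With = N × prevalence; expected failures = group size × failure rate. Entries are rounded.

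| Genotype | N | Prevalence | With | Without | Failure rate | Failures with | Failures without |
|---|---|---|---|---|---|---|---|
| GT1 | 165.3 | 26.8% | 44.3 | 121.0 | 2% | 0.89 | 2.42 |
| GT2 | 57.3 | 79.8% | 45.7 | 11.6 | 2% | 0.91 | 0.23 |
| GT4 | 32.7 | 49.7% | 16.3 | 16.5 | 2% | 0.33 | 0.33 |
| GT5 | 3.3 | 12.9% | 0.4 | 2.9 | 2% | 0.01 | 0.06 |
| GT6 | 11.5 | 54.1% | 6.2 | 5.3 | 2% | 0.12 | 0.11 |
| GT3 | 60 | 22.1% | 13.3 | 46.7 | 8% | 1.06 | 3.74 |
| Total | 330 | | 126.1 | 203.9 | | 3.32 | 6.88 |

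- Failure with: 3.32/126.1 = 2.63%. Failure without: 6.88/203.9 = 3.38%. Risk ratio 0.78; difference 0.74 points.
- GT3 is 13.3/126.1 = 10.5% of the group with and 46.7/203.9 = 22.9% of the group without.

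**Other assumed mixes.** With 85% of the 270 being GT1 (mix B), SVR12 is 97.2% with against 96.8% without: difference 0.43 points, failure odds ratio 0.86. With 35% being GT2 (mix C), it is 97.5% against 96.5%: difference 0.96 points, odds ratio 0.72. Mix A has odds ratio 0.77.

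**False positives.** Analysis 3 states no alpha; 0.05 two-sided is assumed. In 20,000 simulated trials per mix with no effect in any genotype, the pooled Fisher test rejects in 3.7% (A), 2.7% (B) and 5.2% (C). The share rejecting in the protective direction is 3.1%, 1.5% and 4.7%. If all genotypes instead shared a 3.2% failure rate, it would be 1.2%, 1.1% and 1.6%.

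**NS3.** About 5 carriers are expected and the bias is under 0.1 point in every mix.

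**An effect in GT3 only (illustrative rates, mix A).** Let GT3 fail at 20% with and 4.6% without a polymorphism, which keeps GT3 at 8% overall (13.3 × 20% + 46.7 × 4.6% = 4.8 of 60).

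- Within GT3 the risk ratio is 20/4.6 = 4.3 and the odds ratio is (0.20/0.80)/(0.046/0.954) = 5.2.
- Pooled failure is (2.26 + 2.65)/126.1 = 3.89% with and (3.14 + 2.15)/203.9 = 2.60% without. Both the risk ratio and the odds ratio are 1.5.
- The genotype-stratified Mantel-Haenszel odds ratio is 2.1.

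In a simulation of 6,000 trials with GT3 SVR12 of 95% without and 81% with, rejection is 6.6% for pooled Fisher, 16.5% for the stratified exact test and 28.9% in the GT3 row alone.

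**The case against.** The strongest reply is that the plan already holds the right analysis. Results are separated by subtype and tabulated by genotype, and those rows carry no between-genotype confounding. A reader might infer that genotype confounds the resistance results as a whole; the documents do not support that, because only the two total rows are affected.

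The mechanism is also narrower than the spread of prevalences suggests. Protocol 3.0 assumes comparable response across GT1, 2, 4, 5 and 6, so the bias comes only from GT3 against the rest. It would be wrong to say that hard-to-cure subjects fill the group without a polymorphism: that group is 121.0/203.9 = 59% GT1.

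The protocol's A30K result (14/18 at 8 weeks) is not direct evidence either. Protocol 3.0 places the 8-week association in non-cirrhotic subjects, puts the attributable difference between 8 and 12 weeks below 1%, and A30K is a single substitution that Analysis 2 examines within subtype.

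Finally, much of the attenuation in the GT3-only example is dilution, which stratification only partly recovers, and the GT3 row already in the plan does better. The analysis is exploratory and outside the fixed sequence in SAP 10.2.

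All of this stands, and it sets the size of the point. It does not remove it: the total rows are planned and tested, their bias has a predictable direction, and nothing else in the plan adjusts for genotype.

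**Conclusion.** The point holds for the pooled total rows only, as a minor improvement. With no true effect, the NS5A total row is expected to favour polymorphisms by 0.4 to 1.0 percentage points (failure odds ratio 0.72 to 0.86 across three assumed mixes). This rests on the program prevalences applying to this trial, on the 98% and 92% predictions, and on the assumed non-GT3 mix.

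A reader might go further and call the pooled Fisher test invalid or prone to false positives. The figures do not bear that out: its rejection rate with no effect stays at about 3% to 5%. The harm is a slightly biased estimate that can help to hide a GT3 effect. That the total row would be the one quoted is a judgement; the documents do not say so, and Protocol 3.0 itself reports polymorphism impact separately for GT3.

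**What to change.** In SAP 10.8 Analysis 3:

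- Keep Fisher's exact test within each subtype and each genotype.
- For the total rows of both tables, replace it with an exact test stratified by final HCV genotype (exact Cochran-Mantel-Haenszel). Report the stratified odds ratio beside the crude rates, and label the crude totals descriptive.
- State that any polymorphism effect in GT3 is read from the GT3 row, because a common odds ratio still dilutes an effect confined to GT3.

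The cost is a change of test for two total rows and slightly more work in an exploratory table, with no new data. Labelling the crude totals descriptive and dropping their p-value would be the minimum, but it would leave no pooled estimate adjusted for genotype.
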